3.1.2 Primary Outcome Variable

Flow-mediated dilation (FMD) of the brachial artery following 5 minutes of forearm occlusion will be measured using our ultrasound machine (8L-RS 4.0-13.0 MHz probe, Vivid q, GE Healthcare, Mississauga, ON) and FMD data will be analyzed using FDA approved software available from Medical Imaging Applications (Coralville, IA, USA). FMD will be calculated as: (peak hyperemic diameter-baseline diameter)/baseline diameter x 100. Peak hyperemic brachial arterial velocity (and subsequently shear stress) will be determined using Doppler ultrasound, and used for normalization of FMD.

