3.1.3 Secondary Outcome Variables

Arterial stiffness will be assessed using tonometry (Complior, Alam Medical, Saint Quentin Fallavier, France) and reported as PWV in m/s. Arterial stiffness will be determined using carotid – radial pulse wave velocity (PWV), and PWV will be calculated from measurements of pulse transit time and the distance traveled by the pulse between recording sites. Systemic inflammation and immune response will be assessed via antecubital venipuncture and analyzed at the University of Alberta. Based on prior research, important biomarkers have been identified as being involved in the inflammatory process of asthma, and are useful in identifying specific atopic phenotypes.¹⁶ The biomarkers being analyzed will include C-reactive protein (CRP), eosinophils, neutrophils, periostin, interleukin-17 (IL-17), YKL-40, and specific immunoglobulin E (IgE).

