Endothelial function - The endothelial function of the brachial artery will be evaluated after 10 minutes of rest in the supine position using ultrasound imaging (8L-RS 4.0-13.0MHz probe, Vivid q, GE Healthcare, Mississauga, ON). Baseline diameter of the brachial artery will be established, whereby the blood flow of the forearm will be occluded distal to the measuring site for the duration of 5 minutes. Upon release of the occlusion, the blood velocity and the brachial diameter will be monitored for 3 minutes, and later analyzed (Medical Imaging Applications, LLC, Coralville, IA, USA; EchoPAC PC software, version 110.x.x, GE Healthcare, Horten, Norway). Microvascular function will be evaluated as the velocity time integral-envelope of the first heartbeat of reactive hyperemia (VTI; m/s) and the velocity during reactive hyperemia (VRH) calculated as $VTI \times 60/HR$.²³ Shear stress during reactive hyperemia (SSRH) will subsequently then be calculated as $SSRH = 8 \times \text{flow} / \text{diameter}$ and as cumulative SSRH until the time of peak FMD%.^{24,25} FMD corrected for SSRH will be considered the main outcome for endothelial function in this study, and VRH and SSRH as indicators of microvascular function. Follow up tests will be conducted after a 12 hour fasting period when possible. Where applicable, the subjects will be asked to withhold any long-acting asthma medication for a minimum on 48 hours prior to the test, and short-acting asthma medications for 12 hours prior to the test.

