3.4 Statistical Plan

3.4.1 Sample Size Determination

While the impact of asthma exacerbations on vascular function is currently unknown, we based our sample size calculation on our preliminary VTI data from 11 confirmed asthmatics who underwent a mannitol airway challenge to induce airway inflammation and bronchoconstriction. Based on these data, a total of 36 asthmatics and 36 controls in each group (stable asthma, healthy) would be sufficient to detect a 13% difference between these groups in VTI. Our preliminary data show a large increase in CRP in asthmatics experiencing an exacerbation vs. stable patients (7.3 vs. 0.5 mg/L, $p<0.05$), which would correspond to a substantial increase in CV risk³⁵, and be detectable with this sample size. An additional 8 participants per group will be recruited (i.e. 44 asthmatics, 44 stable asthmatics, and 44 controls) to compensate for potential dropouts. Sub-analyses evaluating potential sex-based differences will be exploratory and results will be considered hypothesis-generating.

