3.4.2 Statistical Methods

The mean differences in FMD, systemic inflammation, and arterial stiffness for ED visit compared to the control group will be evaluated using an unpaired t-test. A within-factors repeated measures analysis of variance (ANOVA) will evaluate the mean differences between each assessment day for the exacerbation group to assess change in endothelial function during exacerbation as well as the recovery period. A similar evaluation will be used for arterial stiffness and systemic inflammation/immune response. A one-way analysis of covariance (ANCOVA) will be used to correct for shear rate in FMD for all groups, with both values being reported. An α -level of 0.05 will be used as the significance level for all statistical analysis, and all results will be reported as mean \pm standard deviation unless indicated otherwise.

4 Data Handling and Record Keeping

Data to be collected:

Outcome variables:

Endothelial function

Source of the data: Flow-mediated dilation test (see *measurement, endothelial function* above).

Time point for collection: Collected as the last assessment during the ED visit. For the 2 follow up visits, FMD will be done after arterial stiffness and prior to blood draw.

Who will collect the data: All data will be collected by trained research staff associated with the study.

Why the data is being collected: To evaluate the influence of acute asthma exacerbation on vascular health.

Is the data from a standardized tool: Yes.

What form will the data will take (e.g. binary, continuous (numeric), time to event): Continuous.

Arterial stiffness

Source of the data: pulse wave velocity test (see *measurements, arterial stiffness* above).

Time point for collection: At the ED, arterial stiffness will be collected after blood draw and prior to endothelial function. At the follow up visits, it will be collects as the primary assessment.

Who will collect the data: All data will be collected by trained research staff associated with the study.

Why the data is being collected: To evaluate the influence of acute asthma exacerbation on vascular health.

Is the data from a standardized tool: Yes.

What form will the data will take (e.g. binary, continuous (numeric), time to event): Continuous.

Systemic inflammation and immune response

Source of the data: Venous blood samples (see *measurements, systemic inflammation and immune response* above).

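### The formula for velocity during reactive hyperemia (VRH), VTI × 60/HR, does not give a velocity, so VRH changes with heart rate even when the true velocity is the same

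*Combined protocol and SAP*

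**What the plan says.** Section 3.3 (Measurements, Endothelial function) takes VTI as the "velocity time integral-envelope of the first heartbeat of reactive hyperemia (VTI; m/s") and then defines "the velocity during reactive hyperemia (VRH) calculated as $VTI \times 60/HR". It gives no unit for VRH. The same paragraph names "VRH and SSRH as indicators of microvascular function", and calculates SSRH as 8 × flow / diameter without saying what flow is.

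Section 3.1.2 describes a different input for shear: "Peak hyperemic brachial arterial velocity (and subsequently shear stress) will be determined using Doppler ultrasound, and used for normalization of FMD". VRH is not listed as an outcome in Section 3.1.2 or 3.1.3, and Section 3.4.2 schedules no test of it. The sample size in Section 3.4.1 rests on VTI, not VRH: the planned numbers "would be sufficient to detect a 13% difference between these groups in VTI".

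The only heart-rate field in the data sheet shown (Appendix 5) is in bpm and sits with the triage vital signs.

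**The concern.** A quantity called a velocity should have units of distance over time. Multiplying by 60/HR multiplies by the beat duration, whereas turning a per-beat integral into a mean velocity means dividing by it. The m/s label on VTI does not rescue the formula, because a mean velocity needs no heart-rate factor. Nothing elsewhere in the documents redefines VRH or presents 60/HR as a deliberate heart-rate adjustment.

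If the formula is followed, visits or groups with different heart rates will show different VRH with no difference in hyperemic velocity. The study compares patients after emergency treatment with their own follow-up visits and with controls. If heart rate is higher at the emergency visit (an assumption; the documents give no rates), VRH would look reduced during the exacerbation for that reason alone.

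**Working it through.** **Inputs.** VRH = VTI × 60/HR and the printed VTI unit of m/s (Section 3.3); HR in bpm (Appendix 5). The plan states no numerical VRH, so there is no figure to reproduce. All heart rates below are assumed.

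**Units.** 60/HR = (60 s/min) / (beats/min) = seconds per beat, written T.

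- VTI in m: m × s = m·s.
- VTI in m/s: m/s × s = m.

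Neither is a velocity. With VTI in m, VTI / T = VTI × HR/60 is in m/s. With VTI already in m/s, multiplying by HR/60 would give m/s², so no factor is right.

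**Dependence on heart rate.** Hold the true beat-mean velocity V fixed.

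- VTI in m: VTI = V × T, so written VRH = V × T² = V × (60/HR)².
- VTI in m/s: VTI = V, so written VRH = V × T = V × 60/HR.

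The written value equals V only at 60 bpm.

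**Worked example, V = 1.000 m/s.**

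| HR (bpm) | T (s) | True integral (m) | Written VRH, VTI in m | Written VRH, VTI in m/s | Integral × HR/60 |
|---|---|---|---|---|---|
| 70 | 0.857 | 0.857 | 0.735 | 0.857 | 1.000 |
| 80 | 0.750 | 0.750 | 0.5625 | 0.750 | 1.000 |

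False change, 80 versus 70 bpm: 0.5625/0.7347 − 1 = −23.4% (VTI in m); 0.750/0.857 − 1 = −12.5% (VTI in m/s).

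**Range.** False change = (HRref/HR)² − 1 for VTI in m, or HRref/HR − 1 for VTI in m/s.

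| HR versus HRref (bpm) | VTI in m | VTI in m/s |
|---|---|---|
| 70 vs 60 | −26.5% | −14.3% |
| 80 vs 70 | −23.4% | −12.5% |
| 90 vs 80 | −21.0% | −11.1% |
| 60 vs 70 | +36.1% | +16.7% |
| 90 vs 70 | −39.5% | −22.2% |
| no difference | 0 | 0 |

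**For scale only.** Section 3.4.1 treats 13% (in VTI) as a difference worth detecting. A 13% false fall in VRH needs HR = HRref/√0.87 (VTI in m) or HRref/0.87 (VTI in m/s). For HRref of 60, 70 and 80 bpm this is 64.3, 75.1 and 85.8 bpm, or 69.0, 80.5 and 92.0 bpm. That is 4.3 to 5.8 bpm higher, or 9.0 to 12.0 bpm higher. It says nothing about the study's power, which does not rest on VRH.

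**The case against.** The strongest reply is about consequence. VRH is not a listed outcome, has no planned test and does not drive the sample size. No text says that it feeds the shear correction, and Section 3.1.2 points to a measured peak velocity instead. The formula may be a slip for HR/60, correctable from stored data. This stands as a limit on the point. It does not remove it, because an analyst would code the formula as printed, and the m/s label on VTI would still have to be reconciled with a corrected one.

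A second reply is that the percentages assume equal beat-mean velocity. If the integral in metres were equal instead, going from 70 to 80 bpm would change the written VRH by 70/80 − 1 = −12.5%, while VTI × HR/60 would change by 80/70 − 1 = +14.3%. Part of the 23.4% is also the integral's own dependence on heart rate (0.857 to 0.750 m, −12.5%). Both statements are correct. But VRH is named as a velocity, so equal velocity is the fair condition for testing it. The written factor compounds the dependence that it should remove.

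A third reply is that, with VTI in m/s, the product is a legitimate per-beat integral under the wrong name. That is true, and the 12.5% is then false only when the number is read as a velocity. The plan's name for it invites exactly that reading.

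**Conclusion.** The concern holds. As written, VRH is not a velocity under either reading of VTI, and it varies at equal true velocity as 1/HR² (VTI in m) or 1/HR (VTI in m/s). For a visit 10 bpm faster than 60 to 80 bpm, the false fall is 21.0% to 26.5% or 11.1% to 14.3%. With no heart-rate difference it is zero. The unit error rests on the documents alone; the sizes rest on assumed heart rates.

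The effect is confined to VRH as a microvascular indicator. SSRH and SSRH-corrected FMD, which Section 3.3 makes the main endothelial outcome, would be affected only if VRH were used as flow. The documents do not say that it is, so no size is claimed for that route. The formula should be corrected before analysis.

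**What to change.** State the unit of VTI as the software exports it. If it is a distance, define VRH = VTI × HR/60, using the heart rate of the analysed beat. If it is a mean velocity, report it without a heart-rate factor.

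Two clarifications belong in the same edit, although the point does not depend on them. State that flow in 8 × flow / diameter is a velocity, and name which one. Since that expression has no viscosity term, call the result shear rate, as Section 3.4.2 does: "A one-way analysis of covariance (ANCOVA) will be used to correct for shear rate in FMD for all groups".

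The VRH correction is one line in the protocol and in any analysis code that uses it. If VTI is a distance, heart rate must be read from the ultrasound recording of the analysed beat, because the triage value belongs to another moment. The shear wording also touches Section 3.1.2 and the other uses in Section 3.3.

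### The shear term that corrects the main outcome is written as 8 × flow / diameter with flow undefined; read as volume flow, it is not a shear

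*Combined protocol and SAP*

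**What the plan says.** Section 3.3 (Measurements, Endothelial function) computes shear during reactive hyperemia (SSRH) as "SSRH = 8 \times \text{flow} / \text{diameter" and also as a cumulative value up to peak dilation. No definition of flow and no unit for SSRH is given. The quantity has two uses: "FMD corrected for SSRH will be considered the main outcome for endothelial function in this study", and "VRH and SSRH as indicators of microvascular function".

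Three other statements bear on what flow means:

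- Same paragraph of 3.3, on what is recorded after cuff release: "the blood velocity and the brachial diameter will be monitored for 3 minutes". Volume flow is not listed as a measurement. Earlier in the paragraph the word appears in its ordinary sense: "the blood flow of the forearm will be occluded distal to the measuring site".
- Section 3.1.2: "Peak hyperemic brachial arterial velocity (and subsequently shear stress) will be determined using Doppler ultrasound, and used for normalization of FMD".
- Section 3.4.2: "A one-way analysis of covariance (ANCOVA) will be used to correct for shear rate in FMD for all groups, with both values being reported".

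So shear is built from flow in 3.3 and from velocity in 3.1.2. It is called a stress in both of those sections and a rate in 3.4.2.

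**The concern.** Wall shear rate in a tube is proportional to velocity divided by diameter. An analyst who follows 3.3 to the letter can compute volume flow from the recorded velocity and diameter, put it into the formula, and obtain a number that is not a shear. That number would then be the ANCOVA covariate for the main outcome and would also be reported as a microvascular indicator.

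The paragraph uses separate words for blood flow and blood velocity, so the literal reading is a natural one. Even if it was not intended, the text lets two analysts build covariates with opposite dependence on diameter from the same recordings. Section 3.1.1 states that blinding is not applicable, so this choice should not be left open until data have been seen. Artery diameter enters the FMD denominator, and it may differ between sexes (section 3.4.1 plans exploratory sex analyses) or between visits.

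**Working it through.** The plan gives a formula here and no numerical result, so there is no figure to reproduce. The check covers dimensions first, then consequences.

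**Inputs.** From the protocol: the SSRH formula, the recorded signals (velocity, diameter) and VRH = VTI × 60/HR (all 3.3), and the ANCOVA (3.4.2). Assumed, because the protocol gives no values: velocity V = 0.5 m/s, diameters D of 3 to 5 mm, and coefficients of variation (CVs) of 10–40% for V and 10–20% for D.

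**1. Dimensions.** Volume flow is Q = V × πD²/4. For mean velocity V, wall shear rate under Poiseuille flow is 8V/D = 32Q/(πD³), in 1/s.

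- Flow read as volume flow: 8Q/D = 8 × V × πD²/4 / D = 2πVD, in m²/s. This is neither a rate nor a stress. It equals the true shear rate times πD²/4.
- Flow read as flow velocity: 8V/D, in 1/s. This is a valid shear rate.

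**2. Equal velocity, V = 0.5 m/s.**

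| D (mm) | 8V/D (1/s) | 8Q/D = 2πVD (m²/s) |
|---|---|---|
| 3 | 1333 | 0.0094 |
| 4 | 1000 | 0.0126 |
| 5 | 800 | 0.0157 |

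From 3 to 5 mm, true shear rate falls by 1 − 3/5 = 40%. The literal quantity rises by 5/3 − 1 = 67%.

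**3. Equal volume flow.** From 4 to 5 mm, 8Q/D falls to 4/5 = 0.80 of its value and true shear rate falls to (4/5)³ = 0.51. Both fall, at different rates, so the reversal in step 2 is specific to equal velocity.

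**4. What ANCOVA does with the literal covariate.** Suppose FMD is linear in log true shear with slope b, there is no real group effect, and V and D are independent and log-normal with log-variances sV² and sD², where s² = ln(1 + CV²). Apart from constants, log true shear is log V − log D and the log literal quantity is log V + log D. The fitted within-group slope on the literal covariate is then b × r, with r = (sV² − sD²)/(sV² + sD²). This r is also the correlation between the two quantities.

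- CV 40% for V, 10% for D: r = (0.14842 − 0.00995)/(0.14842 + 0.00995) = +0.87.
- Equal CVs: r = 0.
- CV 10% for V, 20% for D: r = (0.00995 − 0.03922)/(0.00995 + 0.03922) = −0.60.

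If groups differ by δ in log diameter at equal velocity, the unadjusted difference is −bδ and the adjusted one is −bδ(1 + r). The multiplier is 1.87, 1.00 and 0.40 in the three cases, so the spurious difference is enlarged, unchanged, or partly removed. If groups instead differ in log velocity at equal diameter, the multiplier is 1 − r, or 0.13, 1.00 and 1.60. With the correct covariate it would be 0 in every case.

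**5. The velocity to insert.** VRH is the velocity defined just before SSRH. One beat lasts 60/HR seconds, so mean velocity from a per-beat VTI in metres is VTI × HR/60. The printed VTI × 60/HR differs from this by a factor of (60/HR)²: 1.00 at 60 bpm, 0.56 at 80, 0.36 at 100 and 0.25 at 120. VTI is also labelled m/s, so the intended quantity needs checking. The factor 8 presumes mean velocity. Under a parabolic profile an envelope (peak) velocity needs 4 instead, which is only a constant and leaves the ANCOVA adjustment unchanged.

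**6. What is not affected.** FMD in 3.1.2 uses diameters alone, and 3.4.2 reports it with and without correction. The 36 per group in 3.4.1 (44 with dropout) rests on a 13% difference in VTI and does not use SSRH.

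**The case against.** The strongest case on the other side is that flow is simply a slip for flow velocity. The protocol never defines, measures or calculates volume flow. SSRH follows directly after a velocity, and 3.1.2 goes from velocity to shear in the same order. On that reading the formula is 8V/D and nothing is reversed. The sources cited for the calculation are not available here, so they cannot settle the meaning. This objection stands as far as intent goes. It does not remove the fault in the text, which leaves the term undefined and without units.

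A reader might infer something stronger: that the plan corrects every diameter difference in the wrong direction. The documents do not support that. It requires volume flow to be what is applied and velocity to be equal, and it requires a correction whose direction is fixed in advance, such as dividing FMD by SSRH. Section 3.1.2 speaks loosely of normalization, but 3.4.2 specifies ANCOVA, which estimates its own slope. Step 4 shows the bias can then be enlarged, unchanged or reduced.

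The stress-versus-rate wording is mostly terminology. No viscosity is measured, and a constant viscosity would only rescale the covariate.

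**Conclusion.** The formula has to be corrected before analysis because it defines the adjustment of the declared main outcome. Read literally it gives 2πVD, which is not a shear, and at equal velocity it rises with diameter where true shear rate falls. It also disagrees with 3.1.2 and 3.4.2. If it is applied that way, both the ANCOVA covariate and the SSRH microvascular indicator are the wrong quantity.

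The size and direction of the resulting bias cannot be fixed from the documents. Under the assumed CVs and the log-linear model, the literal covariate correlates with true shear anywhere from −0.60 to +0.87. The 40% fall against the 67% rise illustrates the diameter dependence at assumed values and does not forecast the error in this study. The fault is a definition error in the text. The documents do not show that a reversed correction will be carried out.

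**What to change.** In the endothelial-function paragraph of 3.3:

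- Replace the formula with: shear rate = 8 × mean blood velocity / diameter (1/s). Define cumulative shear as its time integral from cuff release to peak diameter.
- Name the Doppler velocity signal used, the same one for all groups and visits. If it is the envelope velocity, say so.
- Do not insert VRH as printed until VTI × 60/HR and the unit of VTI have been checked. Swapping one word for another without this could bring in a heart-rate error.

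Use the term shear rate consistently in 3.1.2, 3.3 and 3.4.2.

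The cost is a few words of protocol text. Velocity and diameter are already recorded and analysed later, so no new measurement is needed and no data are lost if the change is made before analysis.

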Systemic inflammation and immune response – Serum CRP, IgE, periostin, YKL-40 and whole blood eosinophils, neutrophils, and IL-17 will be analyzed from venous blood collected at each assessment day at the end of the visit via antecubital venipuncture by a certified phlebotomist following specified guidelines.²⁶ With the participant sitting in a relaxed position, the upper arm will be occluded to increase the accessibility of the blood vessels. Once a vein is chosen (based on proximity to the surface, size, position and absence of scar tissue and/or pulsation), a sterile 25-gauge needle will be inserted at a 30-degree angle or less to initiate blood draw. Blood will be collected in anti-coagulant-free polypropylene tubes pre labeled with the participant's identification number, date and time, and visit number. After two tubes are collected, the tourniquet will be removed followed by the needle and pressure will be applied to the venipuncture site and held until the bleeding stops. Once collected, the blood will be left to clot for a minimum of 30 minutes followed by centrifuging at 1000g for 10 minutes at 4 degrees Celsius. The serum will be separated into aliquots of 75 µg immediately after centrifuging and then stored at -80 degrees Celsius until analysis. Analysis of inflammatory and immune markers will be completed at the University of Alberta.

Physical activity - Physical activity will be evaluated by step count using a Fitbit activity monitor (Fitbit Inc., San Francisco, CA). Participants will be instructed to wear the monitor on their wrist for 7 days, beginning the morning after Day 2 testing. It will only be removed to shower/bathe and to sleep. Total steps in each 24-hour period will be averaged and used to determine activity levels during the first week of recovery. Low active will be defined as <7,500 steps/day. Somewhat active will be defined as 7,500-9,999 steps/day. Active will be defined as > 10,000 steps/day.²⁷

Pulmonary function – all participants will undergo a full pulmonary function test, according to established clinical guidelines.^{19,20} The expiratory volume in 1 second (FEV₁) responses to

4x100 mg Salbutamol will be evaluated, and an increase in FEV₁ of $\geq 12\%$ and 200 ml will be considered positive for significantly reversible airway constriction.²⁸

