Appendix 4. Budget

1. Salaries and Benefits

Research Assistant: Funds are requested for the salary one research assistant (0.25 full-time equivalents, FTE). This person will assist with data collection for all aims and ensure quality control of all data collection and data analysis.

FTE	1.0	0.25
Salary (Grade 6, Step 5):	\$46,155	\$11,539
Benefits (23%):	\$13,786	\$3,447
Total Salaries and Benefits		\$14,985

2. Material and Supply

Systemic Inflammatory Markers: Venous blood will be collected and processed for whole blood and serum analysis at each assessment for asthmatics and controls (3 assessments (asthma) X 44 participants + 2 assessments(controls) X 44 participants= 220 samples) for analysis of serum CRP, IgE, periostin, YKL-40 and whole blood eosinophils, neutrophils, and IL-17

Blood collection supplies (vacutainers, alcohol wipes, needles)	\$500
Blood analysis	\$9,698
Total Systemic Inflammatory Markers	\$10,198

Other Supplies: A PFT will be performed on all participants to determine lung function and confirm asthma. Each PFT will cost 50\$ and will be performed in all participants (n=88). Including ultrasound jelly, mouthpieces, and nose clips.

	\$4,900
Total Other Supplies	\$4,900
Total Material and Supplies	\$15,098

3. Payment to Study Subjects

Parking and Honoraria: All research participants will be reimbursed for parking at the University of Alberta East Parkade (3 assessments (asthma) X 44 participants + 2 assessments (control) X 44 participants= 220 visits). Participants who complete all parts of the study will receive a \$200 gift card (on average - \$25/visit) at their choice. Honoraria for controls will be a 20\$ gift card after completion of the study, and for asthma participants they will be able to keep the Fitbit used during the study valued at 125\$ (20\$ X 44 participants + 125\$ X 44 participants).

Parking (\$20/day)	\$4,400
Honoraria (\$200/subject)	\$6,380
Total Payment to Subjects	\$10,780

4. Publication Cost

Publications:

Paper 1	\$1,000
---------	---------

Total Publications	\$1,000
5. Summary	
Salaries and Benefits	\$14,985
Materials and Supplies	\$15,098
Payment to Subjects	\$10,780
Publications	\$1,000
TOTAL BUDGET	\$41,863

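### The only blood procedure given yields serum alone, so the planned whole-blood eosinophil and neutrophil counts cannot be obtained as written, and the IL-17 specimen is mismatched

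*Combined protocol and SAP*

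**What the plan says.** The entry on systemic inflammation and immune response in section 3.3 (Measurements) opens by giving each marker a specimen: "Serum CRP, IgE, periostin, YKL-40 and whole blood eosinophils, neutrophils, and IL-17 will be analyzed from venous blood collected at each assessment day". Four markers are therefore serum measures and three are whole-blood measures.

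The same entry then describes the draw and the handling:

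- Tube: "Blood will be collected in anti-coagulant-free polypropylene tubes". No other tube type is named.
- End of the draw: "After two tubes are collected, the tourniquet will be removed followed by the needle".
- Handling: "Once collected, the blood will be left to clot for a minimum of 30 minutes followed by centrifuging at 1000g for 10 minutes".
- Storage: the serum is divided into aliquots "immediately after centrifuging and then stored at -80 degrees Celsius until analysis".

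Appendix 4 (Budget) confirms that both specimens are wanted: "Venous blood will be collected and processed for whole blood and serum analysis at each assessment". Section 3.1.3 lists all seven markers under the secondary outcome variables but gives no specimen or handling detail.

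**The concern.** The opening sentence of the entry requires whole blood for three markers, while the steps that follow leave only serum. A differential white cell count needs cells in suspension. Once blood has clotted, the cells are held in the clot, and frozen serum contains none to count.

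The description is detailed down to needle gauge, insertion angle, clotting time, spin force and temperature, so research staff could reasonably follow it step by step. If they did, two secondary outcomes would be missing for every participant. The loss would be permanent. The ED draw is the only sample taken at the time of the exacerbation, and neither a later visit nor the freezer can replace it.

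**Working it through.** No power or test calculation applies. The check follows the specimen from tube to freezer, compares the result with what each marker needs, and then looks for a repair elsewhere in the document.

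**Step 1. What the procedure leaves**

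| Step in section 3.3 | What remains |
|---|---|
| Anticoagulant-free tubes, two per draw | Blood that will clot |
| Clotting for at least 30 minutes, no tube or portion exempted | Clot plus serum |
| Centrifuging at 1000g for 10 minutes | Separated serum |
| Aliquots frozen at -80 °C | Serum only |

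**Step 2. What each marker needs**

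| Marker | Specimen named | Available after these steps? |
|---|---|---|
| CRP, IgE, periostin, YKL-40 | Serum | Yes |
| Eosinophils, neutrophils | Whole blood | No |
| IL-17 | Whole blood | Not as named; serum is kept |

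IL-17 differs from the cell counts. It is a soluble cytokine and could in principle be assayed in the stored serum, so its fault is a mismatch of specimen and not a certain loss.

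**Step 3. Whether another section supplies the missing step**

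- Section 3.1.3: lists the markers only.
- Section 4 (Data Handling): gives the source as venous blood and the order of collection within each visit, but no tube or processing step.
- Appendix 4: states that whole-blood analysis is intended. Its supplies line covers vacutainers, wipes and needles without naming an additive, and the $9,698 for blood analysis is not broken down by marker or specimen.
- Appendix 5: the ED form has a blood panel tick box among the medical interventions. It is not described as the source of study counts and would not cover the follow-up or control visits.

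None of these gives an anticoagulated tube, a whole-blood handling step or a counting method.

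**Step 4. Size**

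- Markers unobtainable as written: 2 of 7, and 2/7 = 29%.
- Markers with a specimen mismatch only: 1 of 7 (IL-17).
- Draws at the recruitment target of 44 per group (section 3.4.1), with three visits for the exacerbation group and two for each control group: 44×3 + 44×2 + 44×2 = 132 + 88 + 88 = 308.
- Appendix 4's own figure: 44×3 + 44×2 = 132 + 88 = 220. This reproduces the budgeted count and shows that it includes one control group.
- At the 36 per group that section 3.4.1 calls sufficient: 36×3 + 36×2 + 36×2 = 108 + 72 + 72 = 252.

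The defect is the same at any of these totals.

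**The case against.** The best reply is that a tube was simply left out of the description. Appendix 4 plainly intends whole-blood work, and the section 3.3 entry is loosely drafted in other respects: serum aliquots are given in µg, a unit of mass, and no draw volume or assay is stated. Nor does the text say that every tube is clotted. On this view a competent laboratory would add the right tube unprompted.

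Much of this stands. Omission is the likely cause, and nothing in the documents suggests a decision against whole blood. A reader might infer that the counts will certainly be lost at all visits. The documents cannot show that, because staff may notice the gap. What they show is that the written steps do not produce the counts. The reading that all the blood is clotted is an inference, but a firm one: only one tube type is named, two tubes complete the draw, and no exception is made. Calling for anticoagulant-free tubes and then ending the draw is more than silence; it specifies a tube unsuited to cell counts.

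Two stronger readings are also tempting, and the documents do not support them:

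- That 3 of 7 markers are lost. This counts IL-17, which may be recoverable from serum.
- That the secondary objective fails. Section 2 words that objective as arterial stiffness and systemic inflammation; immune response enters only with the outcome variables and measurements. PWV is untouched, and CRP, the only blood marker mentioned in the sample size section, is measured in serum.

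**Conclusion.** The point holds in limited form. Section 3.3 and Appendix 4 plan whole-blood measures, and the only procedure given cannot deliver two of them. Followed as written, eosinophil and neutrophil counts (2 of 7 secondary biomarkers) are unobtainable at every visit, including the unrepeatable ED draw. For IL-17 the named and retained specimens disagree. The primary outcome (FMD), PWV, CRP, IgE, periostin and YKL-40 are unaffected, and the power statement does not depend on the correction.

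The figure of 308 draws is a ceiling that assumes full recruitment at 44 per group and full attendance. The conclusion also assumes that the procedure is carried out literally and that no separate laboratory manual supplies the missing step; the document refers to none. The correction should be made before recruitment, because later discovery would not restore the missing counts.

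**What to change.** In section 3.3, under systemic inflammation and immune response:

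1. Add to each draw an anticoagulated tube, kept unspun, for the eosinophil and neutrophil counts. State the anticoagulant, volume, maximum time from draw to count, and counting method.
2. Limit the clotting, centrifuging and freezing steps to the serum tubes.
3. Correct the tube type and number per draw.
4. State whether IL-17 is measured in whole blood or serum, and by which assay. If serum is chosen, amend the opening sentence of the entry and the matching line in Appendix 4.

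Adding a tube is safer than converting one of the two serum tubes. The document gives no tube or assay volumes, so it cannot be shown that a single serum tube would be enough for the four serum markers.

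The cost is one more tube from the same venipuncture and prompt counting after each draw, ED visits included. Whole-blood analysis is already budgeted in Appendix 4, although that budget is sized for 220 samples and should be checked against the three-group design.
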